#### **VIII. Subgroup Analyses**

We will evaluate treatment difference in the subgroups defined by the following stratification variables:

- a. Sex: Male vs. Female, defined as per stratification
- b. Fracture type: Femoral neck vs intertrochanteric/subtrochanteric, defined as per stratification
- c. Country of enrollment: Canada vs US
- d. Need for assistive devices to ambulate prior to fracture: present vs. absent
- e. Age category: “oldest old” (85 years and over) vs all others
- f. History of Alzheimer’s disease or other dementia: present vs absent
- g. History of chronic obstructive pulmonary disease or asthma: present vs absent
- h. History of coronary artery disease or prior myocardial infarction: present vs absent
- i. Community residence prior to fracture: home or independent living retirement home vs nursing home, rehabilitation or acute care hospital vs other.

The first step will be to test for interaction between treatment and variable defining the subgroups. Analysis within subgroups will be performed for any variable showing an interaction yielding a p-value of 0.20 or less. Subgroup analyses will be analyzed similarly as for primary analysis.

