## **II. Quality Control Prior to Unblinding**

Prior to unblinding, we will review the distributions of each variable to be included in the analysis, aggregated across treatment arms, to identify any outlying values that may be inaccurate and should be checked. To the extent possible, inaccuracies will be resolved and the database updated with the correct values. Data that are clearly incorrect but cannot be corrected will be excluded from the analyses. Data that are unusual but not impossible, and cannot either be verified or corrected, will remain in the analysis.

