## **IV. General Principles**

All analyses (primary, secondary, exploratory) will adjust for the 2 binary stratification factors, namely sex, fracture type (intracapsular, extracapsular), and country (U.S., Canada sites). Sex, fracture type, and site were the original stratification factors for randomization assignment, but with 46 participating sites, some with very few enrolled subjects, it will not be possible to include site in the stratified analysis. Because there might be systematic differences in health care and insurance use between Canada and U.S. sites, we will add country as an additional stratification factor. We will perform descriptive analyses of results by site to see whether there appear to be any major site-specific effects. Analyses will follow a modified intention-to-treat principle, with sensitivity analyses performed to assess the potential impact of missing values and noncompliance. Subjects who had randomization codes generated due to purely technical errors in operating the database will be excluded from any analysis. Subjects who died before receiving either study treatment will also be excluded from any analysis. Subjects randomized and later found not to meet eligibility criteria will be included in the primary analysis to avoid potential bias due to differential assessment of eligibility. Sensitivity analyses excluding these subjects will be conducted. Subjects who were randomized into the wrong stratum will be analyzed as per-randomization strata. All analyses will use 2-sided tests and an overall significance level of 0.05 as the threshold for statistical significance. We will report nominal p-values for all analyses.

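### The sex and fracture-type subgroups follow the stratum entered at randomization, so patients known to be mis-stratified are reported in the wrong subgroup; the effect is probably small but avoidable

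*SAP*

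**What the plan says.** SAP Section VIII lists nine subgroup variables, items a to i. Two of them are tied to the randomization record: "Sex: Male vs. Female, defined as per stratification" and "Fracture type: Femoral neck vs intertrochanteric/subtrochanteric, defined as per stratification". The other seven carry no such qualifier.

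Section IV (General Principles) says what happens when the randomization entry was wrong: "Subjects who were randomized into the wrong stratum will be analyzed as per-randomization strata".

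Section VIII makes the interaction test a gate for what follows: "Analysis within subgroups will be performed for any variable showing an interaction yielding a p-value of 0.20 or less".

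Section II provides for data cleaning before unblinding: "To the extent possible, inaccuracies will be resolved and the database updated with the correct values". Nothing in Section VIII makes the subgroup definitions for sex and fracture type draw on those corrected values. No sensitivity analysis by actual sex or fracture type is planned.

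**The concern.** Keeping the as-randomized stratum is sound for the stratified primary comparison in Section V, because the analysis then mirrors the allocation scheme. That reason does not carry over to Section VIII. A subgroup analysis asks whether the anesthetic effect differs by the patient's own sex or fracture anatomy. Under the present wording, a man entered as female contributes to the relative risk for women, and a patient with an intertrochanteric fracture entered as femoral neck contributes to the femoral-neck result, even after the error has been recognised.

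Two things are at stake. The subgroup relative risks would describe groups slightly different from those they name. And the interaction test, which decides whether within-subgroup results are produced at all, would lose some power if the errors are unrelated to arm and outcome.

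**Working it through.** The SAP gives no mis-stratification rate, subgroup size or interaction power, so there is no figure of its own to reproduce. What follows is an illustration over assumed values.

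**From the SAP:** subgroups a and b are defined by randomization stratum (Section VIII); known errors are left in place (Section IV); the interaction gate is p ≤ 0.20 (Section VIII).

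**Assumed:** a fraction e of each true category is entered wrongly; the true split is q to 1 − q; errors are unrelated to arm and, within true category, to outcome. The stratum is entered before assignment, which makes independence of arm plausible. Independence of outcome is only an assumption.

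**Step 1. Shrinkage of the between-subgroup difference.** The share labelled A is q* = q(1 − e) + (1 − q)e. The proportion correctly labelled is PPV = q(1 − e)/q* in group A and NPV = (1 − q)(1 − e)/(1 − q*) in group B. The observed difference in treatment effect equals the true difference times PPV + NPV − 1.

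Example, 25/75 split with e = 0.05:
- q* = 0.25 × 0.95 + 0.75 × 0.05 = 0.275
- PPV = 0.2375/0.275 = 0.864
- NPV = 0.7125/0.725 = 0.983
- factor = 0.846

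For a 50/50 split the factor is 1 − 2e.

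| e | 50/50 | 25/75 |
|---|---|---|
| 1% | 0.98 | 0.967 |
| 2% | 0.96 | 0.936 |
| 5% | 0.90 | 0.846 |

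The difference therefore shrinks by about 2% to 6% at error rates of 1% to 2%, and by about 10% to 15% at 5%. The factor is exact for risk differences. It is approximate for relative risks, because the ratio of two mixed risks is not the same mixture of the two ratios.

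**Step 2. Power to pass the 0.20 gate.** Suppose a true interaction that would have 80% power at two-sided 0.20 with correct classification. Its noncentrality is 1.282 + 0.842 = 2.123. Misclassification multiplies this by f = (PPV + NPV − 1) × √[q*(1 − q*)/(q(1 − q))].

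Example, 50/50 split with e = 0.05: f = 0.90, and 2.123 × 0.90 = 1.911. Power = Φ(1.911 − 1.282) + Φ(−1.911 − 1.282) = 0.735 + 0.001 = 0.736.

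| e | 50/50 | 30/70 |
|---|---|---|
| 0 | 80.0% | 80.0% |
| 1% | 78.8% | 78.6% |
| 2% | 77.6% | 77.1% |
| 5% | 73.6% | 72.5% |

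The loss is about 1 to 3 percentage points at error rates of 1% to 2%, and about 6 to 8 points at 5%.

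**The case against.** The strongest defence is that the rule is deliberate, stated in advance and consistent. Section IV sets it as a general principle, and Section VIII says subgroups are analysed in the same manner as the primary analysis. Nothing is left to the analyst. The contrast with the other subgroups proves little: items d to i were not stratification factors, so they have no as-randomized value to follow. All of this stands. The SAP does not contradict itself here, and the point concerns the choice made.

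The defence also notes two costs of changing. First, Section V tests homogeneity across as-randomized strata and may report relative risks within them, so a report could show two slightly different results for nominally the same group. Second, the SAP does not say when or how stratum errors are found. If a fracture-type error is found after assignment, the correction rests on post-randomization review, and Section IV shows concern about that kind of process when it retains ineligible patients. Both are fair, so the change is not free of cost. Labelling answers the first. Fixing the verified values before unblinding, and showing the as-randomized version alongside, largely answers the second.

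A reader might infer something stronger: that these two subgroup analyses are seriously diluted, or that the SAP expects many mis-stratified patients. The document supports neither. Section IV is a contingency rule and gives no count. The effect is small at 1% to 2%, and nothing in the SAP points to higher rates, least of all for sex. Nor is attenuation certain: if misclassified fractures differ in prognosis from the rest, the direction could change.

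**Conclusion.** The point holds as a minor one. Sections IV and VIII together place any patient known to be mis-stratified in the wrong sex or fracture-type subgroup, and the reason for as-randomized strata in the primary test does not justify this. It affects two of nine subgroups and leaves the primary analysis untouched.

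The size depends entirely on an error rate the SAP does not give. On the assumed rates and splits shown, it is slight at 1% to 2% and becomes noticeable at about 5%. The direction, toward no interaction, rests on errors being unrelated to arm and outcome. The case for changing the rule is chiefly that the mislabelling is known and avoidable, since a stratum error can be recognised only by knowing the correct value.

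**What to change.** In Section VIII, items a and b, define the subgroups by actual baseline sex and actual fracture type, as verified in the database before unblinding. Both are pre-randomization characteristics, so the comparison within each subgroup stays randomized. Keep as-randomized strata for the primary Mantel-Haenszel stratification and the Breslow-Day test in Section V. Report the number of patients mis-stratified on each factor, and give the as-randomized version of these two subgroup analyses as a check.

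The cost is a short edit to Section VIII and one repeated analysis for two variables. For recognised errors no new data are needed. The one drawback is that the subgroup definitions would differ slightly from the strata in Section V, so tables should state which definition each uses.
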